PROTOCOL: Legal Evaluation for Greater Access to Cancer Care (LEGAL-CARE): A Randomized Pilot Feasibility Trial of a Legal Navigation Program
Version Date: 2-17-2025

Principal Investigator:

[name] MS
Assistant Professor of Medicine
O'Neal Comprehensive Cancer Center
UAB Department of Medicine
Email: [contact]

Research Team and Key Personnel:

[name], MHS
Associate Professor of Medicine
O'Neal Comprehensive Cancer Center, UAB Department of Medicine
Role: Primary Mentor
Email: [contact]

[name], MBA
Professor of Nursing Family, Community & Health Systems
School of Nursing
Role: Biostatistician Mentor, Trial Design and Data Analysis
Email: [contact]

[name]
Assistant Professor of Medicine
O'Neal Comprehensive Cancer Center, UAB Department of Medicine
Role: Collaborator, Qualitative Methodologies
Email: [contact]

[name], BS
Clinical Research Coordinator, Division of Hematology & Oncology, UAB
Role: Patient Interviews
Email: [contact]

[name]
Statistician and Scientist III
Division of Preventive Medicine, UAB Department of Medicine
Role: Research Analyst
Email: [contact]

1. Study Overview

Background and Rationale:

Despite an adept navigation workforce, the regulatory and legal landscape for patients with cancer has become increasingly difficult to navigate. Many barriers faced by patients are entrenched in local, state, and federal policies that require expertise in both social needs and the law. Our group led the first nationwide study investigating the extent to which patients with cancer encounter unmet legal needs related to disability, employment, health insurance, and financial assistance. The Legal Evaluation for Greater Access to Cancer Care (LEGAL-CARE) is a randomized pilot trial to test the feasibility of a legal navigation program. The goal is to address a critical gap in cancer care where patients carry high unmet legal need.

Study Design:

This is a single arm, pilot feasibility trial where 50 recruited patients will receive monthly outreach from a legal navigator over a 6-month period to address legal hardships during their treatment. This study will take place in UAB's medical oncology clinics and include patients aged 18 or older with newly diagnosed advanced stage cancer (stages III or IV) requiring systemic therapy. We hypothesize the legal intervention will be feasible, acceptable and improve patient outcomes.

2. Objectives

Primary Objective:

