- **Assess the feasibility of implementing a legal navigation intervention:** Defined as a 70% retention rate and 75% completion of survey completion (at 3 and 6 months) during the 6-month intervention period. Retention and completion rates will be summarized with 95% confidence intervals.

Secondary Objectives:

- Assess the acceptability and appropriateness of implementing a legal navigation intervention
- Collect patient feedback through semi-structured interviews to inform future large-scale trials.
- Explore the impact of the legal navigation program on financial toxicity, quality of life, treatment delays, and healthcare utilization.

3. Study Population

Inclusion Criteria:

- Adult patients aged ≥ 18 years.
- Newly diagnosed with advanced-stage cancer (Stage III or IV).
- Requiring systemic therapy.
- Capable of providing informed consent.

Exclusion Criteria:

- Non-melanoma skin cancer or in-situ tumors.
- Patients with prior hospice encounters within the past year.
- Patients who are unable to participate in study procedures.

4. Study Procedures

Sample size:

As a pilot study, no hypotheses are being tested ¹ (<https://www.nccih.nih.gov/grants/pilot-studies-common-uses-and-misuses>) therefore the study sample size is based on budgetary and logistic considerations to evaluate feasibility goals.

Screening and Enrollment:

Eligible participants will be identified during their oncology clinic visits and provided with information about the trial (**please see Appendix A for patient education materials**). After informed consent is obtained (**please see Appendix B for informed consent**), baseline assessments (noted below) will be conducted, before the legal intervention commences.

Data Collection:

[figure not shown]
- **Baseline:** Demographics, medical history, and baseline survey of legal barriers and financial toxicity (COST-FACIT) and quality of life (FACT-G7) (**Appendices C-D**). You need to describe all the surveys, number of questions, and scoring here.

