- **Follow-Up:** Surveys at 3 months and 6 months will assess changes in financial toxicity (COST-FACIT) and quality of life (FACT-G7). Additional surveys at these time points will include Assessing the Feasibility of Intervention (AIM), Intervention Acceptability Measure (IAM), and Feasibility of Intervention Measure (FIM) surveys (**Appendix E**). Information on delays in care (measured in days from first appt in our clinic to first visit for systemic treatment) and healthcare utilization (ER visits, urgent care visits, hospitalizations, ICU-level admissions, and palliative care uptake) will be obtained from the EMR at UAB (**please see Appendix F for EMR collection elements**).
- **Qualitative Interviews:** Conducted at the end of the 6-month intervention period to explore patient experiences and perceptions of legal intervention (**please see Appendix G for interview guide outline**)

Participant Incentives:

Participants will receive \$30 at the end of completion of all surveys, and \$50 for interviews. These incentives may be increased during the study period to maintain participation.

5. Study Intervention

Please see study schema below following details on
Fig – Study Schema

Intervention Overview:

- Participants will receive monthly outreach from a trained legal navigator over a 6-month period. The legal navigator is a lawyer (Juris Doctor, or JD) who will proactively address specific legal barriers the patient may encounter during treatment. Communication will include phone calls (and if requested, virtual consultations) tailored to patient needs. In between legal outreach periods, patients may call the legal navigator team themselves for legal needs that may arise. Legal navigator team will be from Triage Cancer, a

nationwide non-profit organization with a track record of assisting patients with legal barriers following a cancer diagnosis.

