The principal investigator ([name]), and clinical research coordinators ([name] and [name]) will regularly monitor data quality and completeness. An independent data monitoring committee (DMC) will be established to oversee the integrity of the data and patient safety.

7. Statistical Analysis Plan

Primary Outcome:

- **Feasibility:** Defined as a 70% retention rate and 75% completion of surveys (at 3 and 6 months) during the 6-month intervention period. Retention and completion rates will be summarized with 95% confidence intervals.

Sample size: We will recruit 50 patients to assess intervention feasibility, with no power calculation needed as efficacy is not the primary objective ¹. As a pilot study and consistent with NIH guidance, the sample size is not powered for formal statistical inference but was considered based on examining the feasibility and acceptability of the approach and on refining the intervention design and procedures in preparation for a future larger proposal ².

Analytical approach: Led by the [name] (PI) with input from [name] (co-mentor biostatistician) and implemented by staff analyst, [name] (research analyst/statistician).

Assess feasibility of the intervention: Proportions of: a) eligible approached patients that accept to trial participation; b) proportion of participating patients retained at follow-up; and c) proportion of participating patients completing at least 75% of surveys, will be estimated and

confidence intervals will be computed with simple logistic or probit regression models and inverse link transformations. Descriptive statistics and measures of effect size (e.g., Cohen's d, Cramer's V) will be used to explore association between the proportions of interest and participant sociodemographic characteristics and reported legal barrier types.

Secondary Outcomes:

Explore patient perceptions of legal intervention impact: We will use qualitative methodology therefore biostatistical approaches are not applicable. Sampling for qualitative inquires is sequential and targeted to individuals who can provide insights on the processes under study. Typically, pilot qualitative approaches involve ~20 participants and expect to have a sufficient participant pool to carry out the qualitative inquiry ^{3,4}. This sample size follows qualitative research best practices, ensuring thematic saturation while maintaining feasibility within the study timeline. If thematic saturation is not reached, we will increase this number.

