Here we will use repeated measures (baseline, 3 month, and 6 months post-intervention) of survey measures (collected directly) and utilization rates (extracted from EHR). Baseline characteristics and outcomes will be examined with descriptive statistics and measures of effect size. For survey outcome scales (COST-FACIT and FACT-G7), linear mixed-effect models will be fitted with all available data to estimate mean outcomes at each time-point by group. Linear contrasts will be used to estimate mean differences between groups at the follow-up times, adjusted for baseline and 95% confidence intervals will be computed. The models will be of the form $\widehat{Y}_{ij} = \beta_0 + \beta_1 Y_0 + \beta_2 T1 + \beta_3 T6 + \beta_4 LEGAL + \beta_5 T1 \times LEGAL + \beta_6 T6 \times LEGAL + \gamma_i$, where \widehat{Y}_{ij} is the value of an outcome for subject i at time j , β_1 is the coefficient for the baseline outcome value (Y_0), $\beta_0, \beta_2, \beta_3$ are coefficients specific to the reference group (enhanced usual care), $\beta_4, \beta_5, \beta_6$ are coefficients specific to the legal intervention group, $LEGAL$ is a binary indicator of group, $T1$ is a binary indicator for time at 1-month post-intervention, and $T6$ is a binary indicator for 6 months. Linear combinations of model coefficients allow estimation of means by group as well as mean differences. The between-group contrast at 1-month post-intervention (adjusted for baseline) is estimated by $\beta_4 + \beta_5$, and the between-group contrast at 6-months (adjusted for baseline) is estimated by $\beta_4 + \beta_6$. Baseline SDs will be used to rescale the contrasts into standardized measures of effect (Cohen's d). For delays in care, we will use time-to-event analysis methods, such as Cox proportional hazards models, to compare the time from new diagnosis to treatment initiation between enhanced usual care and legal intervention groups. Hazard ratios will be estimated with 95% confidence intervals. For health care utilization measures, generalized linear mixed-effect models will be used. Here, a link-transformation of the expected outcome value is modeled. For discrete count outcomes (e.g. urgent care visits) a default link-transformation is the natural logarithm of the mean, and for binary outcomes (e.g. whether a hospitalization occurred) a default link-transformation is the natural logarithm of the

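### The COST-FACIT and FACT-G7 model puts its first follow-up term and contrast at 1 month, where no survey is scheduled, and has no term for the 3-month survey

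*Protocol*

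**What the plan says.** **Survey schedule.** Section 4 (Data Collection) sets a baseline survey and then states: "Surveys at 3 months and 6 months will assess changes in financial toxicity", with quality of life measured at the same visits. Section 2 (Primary Objective) and Section 7 (Primary Outcome) use the same two follow-up times and place them within treatment: "75% completion of surveys (at 3 and 6 months) during the 6-month intervention period". The FACT-G7 bullet in Section 7 and the data-collection row of Section 11 also list baseline, 3 and 6 months. The detailed model paragraph in Section 7 opens with those times too: "Here we will use repeated measures (baseline, 3 month, and 6 months post-intervention) of survey measures".

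**Model.** The same paragraph then says that "linear mixed-effect models will be fitted with all available data to estimate mean outcomes at each time-point by group". The formula has seven fixed-effect terms: intercept, baseline value Y0, T1, T6, LEGAL, T1×LEGAL and T6×LEGAL. T1 "is a binary indicator for time at 1-month post-intervention"; T6 marks 6 months. Two contrasts are named. The first reads "The between-group contrast at 1-month post-intervention (adjusted for baseline) is estimated by" β4+β5; the second is β4+β6 at 6 months.

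**Design.** Section 1 says: "This is a single arm, pilot feasibility trial where 50 recruited patients will receive monthly outreach from a legal navigator".

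**The concern.** The model's first follow-up time does not match any visit. The label appears twice, in the definition of T1 and in the named contrast, and the symbol itself is T1 rather than T3, so it is not a single slipped word. One of the two named contrasts therefore sits where there are no data, and one of the only two follow-up surveys has no term. That conflicts with the paragraph's own aim of a mean for each time point. An analyst would have to depart from the written formula to obtain a 3-month result, and the Cohen's d derived from the first contrast is among the outputs meant to inform a larger trial.

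The post-intervention label is a second part of the same error, because the surveys fall during the intervention and not after it.

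**Working it through.** The protocol gives no computed figure to reproduce here. The check compares the stated visits with the model's columns and asks which contrasts can be estimated.

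**Inputs.** 50 patients (Section 1); surveys at months 0, 3 and 6 (Sections 2, 4, 7 and 11); the seven-term formula of Section 7. Assumptions: every survey is completed and, where two groups are considered, both contain patients. The protocol gives no split; 25/25, 30/20 and 40/10 give the same ranks.

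**Step 1: rows.** 50 × 3 = 150 rows with baseline, or 50 × 2 = 100 follow-up rows. No survey falls at month 1, nor at month 7 if the month is counted from the end of the intervention (6 + 1). T1 is therefore 0 on every row. The 50 month-3 rows have T1 = T6 = 0.

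**Step 2: rank as written, two groups.** The T1 and T1×LEGAL columns are all zero, so the rank is 7 − 2 = 5, with or without baseline rows. β5 multiplies a zero column, so β4+β5 is not estimable; β4+β6 is. If baseline rows are outcomes, month 3 shares its reference level with baseline, and β4 mixes the two times. With follow-up rows only, β4 alone is the 3-month difference, but the protocol does not name it.

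**Step 3: first indicator moved to month 3, and single arm.**

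| Design | Rows | First indicator | Rank of 7 | β4+β5 | β4+β6 |
|---|---|---|---|---|---|
| Two groups | 0, 3, 6 | as written | 5 | no | yes |
| Two groups | 3, 6 | as written | 5 | no | yes |
| Two groups | 0, 3, 6 | month 3 | 7 | yes | yes |
| Two groups | 3, 6 | month 3 | 5 | yes | yes |
| Single arm | 0, 3, 6 | as written | 3 | no | no |
| Single arm | 3, 6 | as written | 3 | no | no |
| Single arm | 0, 3, 6 | month 3 | 4 | no | no |
| Single arm | 3, 6 | month 3 | 3 | no | no |

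On two-group follow-up rows with both indicators kept, the indicators sum to the intercept, and their interactions sum to LEGAL; hence rank 5. Dropping the month-3 indicator and its interaction leaves five columns of rank 5, and the 3-month contrast is then β4. In a single arm LEGAL equals the intercept, so no LEGAL contrast exists under any time coding. A model with only an intercept, a 3-month and a 6-month term, and baseline as an outcome row, has rank 3 of 3.

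**Step 4: why the full-rank version is unsafe.** Rank 7 of 7 needs baseline rows as outcomes while Y0 is also a covariate. On those rows the outcome equals the covariate, so its slope there is 1. In balanced data the common Y0 slope is the average over the three times. If both follow-up slopes were 0.5 (an assumption), it would be (1 + 0.5 + 0.5)/3 = 0.67. For a baseline group difference D, each adjusted contrast would shift by about (0.67 − 0.5) × D = 0.17 D in absolute size.

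**Step 5: the post-intervention label.** Section 11 ends enrolment in month 16 and data collection in month 24. For a patient enrolled in month 16, 6 months from the start is month 22, inside the window. Six months after the intervention ends is 16 + 6 + 6 = month 28, outside it.

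**The case against.** The strongest reply is that the intent is clear. Section 7 says that the contrasts compare the groups at follow-up, Section 4 fixes two follow-ups, and T6 takes the second. T1 can then only be the 3-month visit, and the rank results merely restate a wrong label. This stands as far as intent goes. A reader might infer that the protocol leaves the first contrast undefined, or that a 1-month survey was planned and then left out; the documents support neither. What remains is that the written definition and contrast are wrong, and that the coefficient giving the 3-month contrast depends on whether baseline rows enter as outcomes, so changing the label is not quite enough.

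A second reply is that Section 1 describes a single arm, so no between-group contrast exists and the model must be rewritten anyway. That conflict is real but separate. Resolving it does not correct the time term, because a single-arm change model also needs a 3-month term. Equally, a reader should not blame the time error for losing both contrasts: with two groups β4+β6 survives, and with one arm recoding T1 rescues neither.

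A third reply is that these outcomes are exploratory, no hypotheses are tested, and no bias or loss of precision has been shown. That stands, and it limits the weight of the point.

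**Conclusion.** The point holds in a limited form. The model's first time indicator and first named contrast refer to a time at which the protocol schedules no survey. Taken literally, T1 is 1 on 0 of 150 rows, β4+β5 is not estimable, and the 50 three-month rows have no indicator or named contrast. The row counts assume complete surveys; the loss of β4+β5 does not depend on the group split. Month 3 is the evident intent.

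The effect is confined to COST-FACIT and FACT-G7 as exploratory secondary outcomes; the primary feasibility outcome does not use this model. It is a modest correction, worth making before analysis because it is cheap and removes a departure from the written formula.

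**What to change.** In Section 7:

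- Replace T1 with a 3-month indicator and relabel the 1-month contrast as the 3-month contrast.
- Remove the post-intervention wording from the time points, and have the sponsor state the time origin. The protocol does not define it; consent, baseline survey and first outreach are all possible.
- **If the trial has two groups:** fit follow-up rows only, with Y0 as covariate and month 3 as the reference time, so that the month-3 indicator and its interaction drop out. The 3-month contrast is β4, and the 6-month contrast is β4 plus the T6×LEGAL coefficient. Do not also enter baseline rows as outcomes while Y0 is a covariate.
- **If it is single arm, as Section 1 states:** drop Y0 and all LEGAL terms, keep baseline as an outcome row, and report the 3-month and 6-month coefficients as mean changes from baseline.

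The cost is an edit to Section 7 and the model code. Visits, surveys and sample size do not change.

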Evaluate trajectory of financial hardship, health-related quality of life, delays in care, and health care utilization: Brief description followed by detailed statistical plan

- **Financial Toxicity:** Changes in COST-FACIT scores will be analyzed using linear mixed-effect models.
- **Quality of Life:** FACT-G7 scores will be analyzed at baseline, 3 months, and 6 months, with adjustments for baseline values.
- **Delays in Care:** Time-to-event analysis will be conducted using Cox proportional hazards models, comparing the time from diagnosis to treatment initiation between the two groups.
- **Healthcare Utilization:** Emergency department visits and hospitalizations will be analyzed using generalized linear mixed models. Results will be presented as mean ratios or odds ratios.

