odds ($odds = p/[1 - p]$). Inverse-link transformations will be used to estimate estimated expected values of the outcomes by group at each time-point. For count outcomes, contrasts are estimated as mean ratios, and for binary outcomes contrasts can be estimated as odds ratios (default) or as relative risks (if the model is fitted with a log-link and a robust standard error). 95% confidence intervals will be computed. We will use SAS (version 9.4M8) and R (version 4.4.2) for the statistical analysis of quantitative data.

8. Safety and Adverse Events

Safety Monitoring:

Any adverse events related to the legal intervention will be recorded and reported to the IRB. Although legal navigation is a low-risk intervention, any significant issues related to stress, patient dissatisfaction, or legal complications will be addressed by the study team.

9. Ethical Considerations

This study will be conducted in accordance with the Declaration of Helsinki and Good Clinical Practice (GCP) guidelines. Informed consent will be obtained from all participants, and confidentiality will be maintained. Study approval is on track to be obtained from the UAB Institutional Review Board (IRB).

10. Dissemination of Results

The results of this trial will be published in peer-reviewed journals and presented at major oncology conferences, including ASCO and/or ASCO Quality Care Symposium. Patient-friendly summaries will also be disseminated through advocacy organizations and local clinics. Collaboration with Legal Services Alabama and Triage Cancer will help ensure broader dissemination to policy-makers and healthcare providers.

11. Timeline

Milestone	Timeline
IRB Approval and Protocol Finalization	Pre Grant
Training Phase	Months 1-3
Recruitment Initiation	Month 4
Completion of Enrollment	Month 16
Primary Data Collection (Baseline, 3-month, 6-month)	Months 4-24
Data Analysis	Months 14-26
Manuscript Preparation	Months 24-30
Dissemination	Months 28-36

12. Conclusion:

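### Utilization is introduced as a rate but compared as a mean count with no exposure term, so lost observation time could pass for a change in use

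*Protocol*

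**What the plan says.** In the protocol's Section 7, the detailed paragraph under Secondary Outcomes introduces the measure as "utilization rates (extracted from EHR"), taken at baseline, 3 months and 6 months. It then sets the count model: "For discrete count outcomes (e.g. urgent care visits) a default link-transformation is the natural logarithm of the mean". The contrast follows: "For count outcomes, contrasts are estimated as mean ratios". The summary bullet on Healthcare Utilization agrees: "Results will be presented as mean ratios or odds ratios".

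Section 4 (Data Collection) and Section 6 give the source: "healthcare utilization (ER visits, urgent care visits, hospitalizations, ICU-level admissions, and palliative care uptake) will be obtained from the EMR at UAB". The text shown gives no offset, no exposure time, no length for any count window, and no rule for how death or a move of care ends observation.

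Three further statements bear on the point:
- The population in Section 3 is "Newly diagnosed with advanced-stage cancer (Stage III or IV").
- Study Design in Section 1 describes a single arm of 50 patients, although the title says randomized and Section 7 writes of two groups.
- Section 2 lists utilization among the outcomes to be explored.

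**The concern.** A rate has a denominator. The model and the reported contrast in Section 7 have none, so the outcome is named one way and its contrast is fixed another way. A mean count gives a patient observed for three weeks of a window the same weight as one observed for all of it.

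In advanced cancer it is foreseeable that some patients will die, or move their care away from UAB, within six months. With one arm, the only utilization contrast that can be estimated is change over time, and no concurrent group is there to cancel the lost exposure. If two groups were in fact compared, the loss would cancel only if observation time were equal between them.

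What is at stake is the reading of the ratio. Fewer visits because fewer patient-days were observed could be taken for reduced use during legal navigation, and carried into the planning of the larger trial.

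**Working it through.** The protocol gives no visit rate, mortality or loss figure, so there is no stated figure to reproduce. The inputs below are assumptions, shown over a range.

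**Setup.** Each patient has a constant visit rate *r* while alive and observed, unrelated to the risk of death, and *r* does not change. The expected count in a window is *r* × (time observed in it). A mean ratio without an exposure term therefore equals the ratio of mean observed times. Dividing by observed time returns *r* in every window, so the rate ratio is 1.00.

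**Case 1: deaths at a constant hazard.** Let D be the 6-month mortality and λ = −ln(1 − D)/6 per month. Survival to month 3 is √(1 − D). As a fraction of three months, mean observed time per enrolled patient is:
- months 0–3: A = (1 − √(1 − D)) / (3λ)
- months 3–6: B = A × √(1 − D)

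| D | A | B | B/A = √(1 − D) |
|---|---|---|---|
| 10% | 0.974 | 0.924 | 0.949 |
| 20% | 0.946 | 0.846 | 0.894 |
| 30% | 0.916 | 0.766 | 0.837 |

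B/A is the apparent ratio of months 3–6 to months 0–3 if patients who died before month 3 stay in the second window as zeros.

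If those windows are set missing instead, the mean observed time in months 3–6 is B/√(1 − D) = A, and the ratio is A/A = 1.00 at every D. Against a fully observed baseline window of three months, each follow-up window then gives A, about 0.97, 0.95 and 0.92. With zeros kept, months 3–6 against that baseline give B: 0.92, 0.85 and 0.77.

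**Case 2: a share d lost to observation uniformly over six months.** This is a different loss pattern, against a fully observed baseline of equal length.
- months 0–6: 1 − d/2 = 0.95, 0.90, 0.85 for d = 10, 20, 30%
- months 3–6, zeros kept: 1 − 0.75d = 0.925, 0.85, 0.775
- months 3–6, those gone before month 3 set missing: (1 − 0.75d)/(1 − 0.5d) = 0.97, 0.94, 0.91

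**Simulation check.** This used 50 patients, 2000 replicates, overdispersed counts at an assumed 0.15 visits per month, d = 30% and 6-month windows. The ratio of total counts was 0.85, and the ratio per unit of observed time was 1.00. It compared totals and did not fit the mixed model.

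**The case against.** The strongest reply is that this argues from silence. The text fixes only a default link, and a log link is the one to which a person-time offset attaches. The one written-out model equation is for the survey scales. The word rates points towards a denominator, and details of exposure may stand in an analysis plan or in Appendix F, neither of which is shown. This limits the point but does not remove it: the protocol twice commits to mean ratios as the reported contrast, and a mean ratio is not a rate ratio.

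The reply is right on several stronger readings that a reader might infer:
- **That the look-back windows are unequal.** The documents give no window lengths, so they may be equal. The need is to state them.
- **That a false fall in use will occur.** The size depends on an unstated rule about windows after death, and under Case 1 one reasonable rule brings the ratio of the two follow-up windows back to 1.00. That ratio is also not a contrast the protocol names.
- **That the error must favour the intervention.** This holds only for a constant rate. If visits rise near death, the shift could shrink or reverse.
- **That the retention target measures lost exposure.** The target is "Defined as a 70% retention rate and 75% completion of surveys (at 3 and 6 months) during the 6-month intervention period". Utilization comes from the EMR, so a patient who stops answering surveys may still be observed. Death or leaving UAB care is what ends exposure.

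**Conclusion.** The point holds in a limited form. Section 7 calls the outcome a rate and then reports a ratio of mean counts with no exposure term. In a single-arm stage III or IV cohort, that ratio could move when the visit rate has not.

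Under a constant visit rate and 10 to 30% deaths by six months, the apparent fall from the first to the second follow-up window is about 5 to 16% with zeros kept and nil with those windows missing. Against a full equal-length baseline with those windows missing, it is about 3 to 8%. Mortality, the constant rate and its independence from death are all assumptions, and the net direction is not certain.

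The consequence is modest. Utilization is exploratory, no hypothesis is tested, and the primary feasibility result is untouched. The change is still worth making, because the correction is small and the estimates are meant to inform a larger trial.

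**What to change.** In Section 7, for the count outcomes:
- Add log(days under observation in the window) as an offset, and report rate ratios in place of mean ratios. A patient with no observed days in a window contributes no record for it.
- Use a baseline window of the same length as each follow-up window, and state that length.
- End exposure at death or documented transfer of care. Do not end it at the last EMR visit: that date is itself produced by visits, so it would shorten the denominator most for patients who have none.
- Report the number of deaths, and give the mean count per enrolled patient as a sensitivity analysis.

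Do not restrict the binary outcomes to patients with complete windows, because that conditions on survival.

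The cost is a few sentences and one model term. Dates of death and of transfer must be abstracted. The text shown does not say that they are, so check Appendix F. There is a small downside: the estimand becomes a rate while alive and under observation, not visits per enrolled patient. Hence the death count and the sensitivity analysis.
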